SAD phase will include a sentinel design in which 2 participants at the given cohort dose be initially enrolled. If the dose can be well tolerated for 48 hours after full administration per site Principle Investigator's judgement, the remaining 6 participants will be enrolled to receive a single dose of MBS-COV at the same dose.

The decision for the escalation to the higher dose levels will be made by the study SRC after safety review of available information 7-day post treatment period. The data from SAD phase will be reviewed for safety trends to start MAD phase.

Part B (MAD Phase)

This is a randomized, double-blind, placebo-controlled study in approximately 20 healthy participants. Doses will be selected based on a comprehensive review of the SAD data and estimates of the clinically efficacious dose.

The MAD Phase of the study consists of a screening period followed by multiple dose administrations of MBS-COV or placebo through a portable nebulizer once daily for 7 consecutive days (Day 1 to Day 7). Participants will be followed up for 21 days to assess post-treatment safety.

The decision for the escalation to the higher dose levels will be made by the study SRC after safety review

of available information 7-day post treatment period. Each cohort will include ten participants (8 active and 2 placebo) per table below:

Table 0-2: MAD Phase Cohorts

Cohort		Number of Participants	MBS-COV Dose (mg/kg)	Dose
MAD Phase	B1	8 (MBS-COV) +2 (placebo)	0.6	Once daily for 7 days
	B2	8 (MBS-COV) +2 (placebo)	1.2	Once daily for 7 days

Study Visits:

- **Screening Visit (SV: Up to 28 Days prior to Day 1):** Consists of signing the ICF and study qualification based on evaluation of inclusion/exclusion criteria.
- **Treatment Visit 0 (T0: Day -1):** All participants continuing to meet eligibility criteria will be enrolled into the study and confined to research clinic until Day 2 for cohort A1 to A3 (SAD phase) and Day 9 for cohort B1 to B2 (MAD phase).
- **Treatment Visit 1: Baseline Visit (T1: Day 1):** The first assigned study treatment dose will be administered after completion of all study evaluations. Adverse events and changes in concomitant medications will be collected. Participants in Cohorts A1 to A3 will inhaled a single dose of MBS-COV or placebo through a portable nebulizer on Day 1. Participants in cohort B1 and B2 will receive doses of MBS-COV or placebo by through a portable nebulizer once daily for 7 consecutive days from Day 1 to Day 7.

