This is a randomized, double-blind, placebo-controlled study in approximately 20 healthy participants. Doses will be selected based on a comprehensive review of SAD data and estimates of the clinically efficacious dose.

The MAD Phase of the study consists of a screening period followed by multiple dose administrations of MBS-COV or placebo through a portable nebulizer once daily for 7 consecutive days (Day 1 to Day 7). Participants will be followed up for 21 days to assess post-treatment safety.

The decision for the escalation to the higher dose levels will be made by the study SRC after safety review of available information 7-day post treatment period. Each cohort will include ten participants (8 active and 2 placebo) per table below:

Table 3-2: MAD Phase Cohorts

Cohort		Number of Participants	MBS-COV Dose (mg/kg)	Dose
MAD Phase	B1	8 (MBS-COV) +2 (placebo)	0.6	Once daily for 7 days
	B2	8 (MBS-COV) +2 (placebo)	1.2	Once daily for 7 days

Study Visits:

- **Screening Visit (SV: Up to 28 Days prior to Day 1):** Consists of signing the ICF and study qualification based on evaluation of inclusion/exclusion criteria.
- **Treatment Visit 0 (T0: Day -1):** All participants continuing to meet eligibility criteria will be enrolled into the study and confined to research clinic until Day 2 for cohort A1 to A3 (SAD phase) and Day 9 for cohort B1 to B2 (MAD phase).
- **Treatment Visit 1: Baseline Visit (T1: Day 1):** The first assigned study treatment dose will be administered after completion of all study evaluations. Adverse events and changes in concomitant medications will be collected. Participants in Cohorts A1 to A3 will inhaled a single dose of MBS-COV or placebo through a portable nebulizer on Day 1. Participants in cohort B1 and B2 will receive doses of MBS-COV or placebo by through a portable nebulizer once daily for 7 consecutive days from Day 1 to Day 7.

Part A (SAD Phase)

- **Treatment Visit 2 (T2: Day 2)**
- **Treatment Visit 3 (T3: Day 3)**
- **Treatment Visit 4 (T4: Day 4)**
- **Treatment Visit 5 (End of Treatment) (T5: Day 7)**

- **Follow-Up Visit 1 (FU1: Day 14)**
- **Follow-Up Visit 2 (FU2: Day 28)**

Part B (MAD Phase)

- **Treatment Visit 2 (T2: Day 2)**
- **Treatment Visit 3 (T3: Day 3)**
- **Treatment Visit 4 (T4: Day 4)**
- **Treatment Visit 5 (T5: Day 5)**
- **Treatment Visit 6 (T6: Day 6)**
- **Treatment Visit 7 (T7: Day 7)**
- **Treatment Visit 8 (T8: Day 8)**
- **Treatment Visit 8 (End of Treatment) (T9: Day 9)**

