- **Follow-Up Visit 1 (FU1: Day 14)**
- **Follow-Up Visit 2 (FU2: Day 28)**

If any of the dose escalation stopping criteria have occurred in Part A or Part B, the SRC will make a final recommendation for dose escalation to the next cohort.

- **NOTE:** The dose escalation decision through the study will not be made until the following:
 - (1) All study participants in a given cohort have been enrolled,
 - (2) All such participants have completed Treatment Visit 5 (Day 7) (for SAD-Part A) and Treatment Visit 9 (Day 9) (for MAD-Part B) of the study or withdrawn from the study, whichever occurs first,
 - (3) The SRC will review the available safety data and recommend further dose escalation.

[figure not shown]
Additionally, dose escalation stopping criteria are defined per the below:

- a. Death in any participant in which the cause of death is judged to be possibly, probably or definitely related to MBS-COV.
- b. The occurrence in any participant of a severe local application site reaction (Grade 3 which doesn't resolve or recurs, or Grade 4) that is judged to be possibly, probably or definitely related to MBS-COV.
- c. The occurrence in any participant of a SAE whose causal relationship to MBS-COV is judged to be probably, possibly, or definitely related to MBS-COV.
- d. The occurrence, in two or more participants of Grade 3 AE or laboratory abnormalities, judged to be probably, possibly, or definitely related to MBS-COV.

- e. The occurrence of two of the same AE or laboratory abnormality \geq Grade 3 judged to be probably, possibly, or definitely related to receipt of MBS-COV
- f. The occurrence, in one or more participants of Grade 4 AE or laboratory abnormalities, judged to be probably, possibly, or definitely related to receipt of MBS-COV.
- g. Any pattern of significant symptoms, physical findings, or laboratory abnormalities that, although individually minor, collectively represent a safety concern in the opinion of the investigator and are judged by the SRC to be at least possibly related to MBS-COV.
- h. PK exposure limits of mean AUC of 385.6 h*ng/mL or C_{max} of 141.8 ng/mL for one cohort, whichever comes first.(Single dose: AUC of 386.9 h*ng/mL or C_{max} of 91.7 ng/mL).

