Day	Up to -28	Day -1	Day 1		Day 2-Day 7	Day 8	Day 9 (48 hours after last dosing)	Day 14	Day 28
Window Period			Within 28 days of the Screening Visit		NA	NA	±1	±1	±1
Urinalysis ^[14]	X	X			X	X	X	X	
Nasopharyngeal or Nasal Swab for COVID-19 ^[15]	X	X					X	X	X
Urine Drug and Alcohol Screening	X	X							
PK evaluations ^[16]			X	X	X	X	X		
ADA ^[17]			X					X	X
Screening for infectious diseases (HIV antibody; HbsAg; HCV antibody)	X								
INTERVENTION(s)									
MBS-COV Administration ^[18]			X		X				

[1] Informed consent must be obtained prior to participation in any protocol-related activities that are not part of routine care.

[2] Initial evaluation of participant eligibility will be performed by Investigator.

[3] Medical history and current therapies (medications and non-medications).

[4] Symptom-directed physical examination.

[5] Vital signs will include blood pressure, pulse, respiration rate, and temperature. On treatment visits will be conducted three times a day, within 120 minutes before administration, within 1 hour after administration, and 4-6 hours after administration, respectively. On other visits will be conducted once during the visit.

[6] 12-lead ECG on treatment visits will be conducted three times a day, within 120 minutes before administration, within 1 hour after administration, and 4-6 hours after administration, respectively. On other visits will be conducted once during the visit.

[7] Spirometry assessments will be started 5 minutes after the dosing with frequent spirometry measurements at 5 (± 1 min), 15 (± 1 min), 30 (± 5 min) 60 (± 5 min) minutes. On other visits will be conducted once during the visit.

[8] Participant will be discharge from the clinic when all required assessments for V9 are performed.

[9] If hematology, biochemistry, coagulation and urinalysis are completed within 7 days prior to dosing, this assessment does not need to be repeated on Day-1.

[10] Hematology

Hemoglobin, Hematocrit (HCT), Red Blood Cells (RBC), White Blood Cells (WBC) with total and differential count, Absolute Neutrophil Count (ANC) and platelets.

[11] Biochemistry

Hepatic function indicators: total bilirubin, alkaline phosphatase, aspartate aminotransferase (AST), alanine aminotransferase (ALT), total protein, albumin Lactate dehydrogenase (LDH), amylase and lipase

Renal function indicators: Serum creatinine, eGFR

Electrolytes: sodium, potassium, chloride, calcium and bicarbonate

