4.3.7. Part B (MAD) - Follow-Up Visit 1 (FU1: Day 14)

A Follow-up visit will be performed 1 week (FU1) after last day of study drug administration. To ensure the safety of participants and site staff. The following assessments will be performed:

- Vital signs
- Physical examination
- 12-lead ECG
- Nasopharyngeal or nasal swab for COVID-19
- Laboratory assessments (hematology, chemistry, coagulation and urine analysis)
- ADA timepoints: Blood samples will be collected on Day 14
- Urine pregnancy test
- List concomitant medications
- Adverse events evaluation

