8.5. BLINDING AND PREVENTION OF BIAS

8.6. INTERIM ANALYSIS

There is no efficacy interim analysis planned for this study; however, the safety data from all participants of each completed cohort will be reviewed by the SRC prior to enrolment of further participants or dose escalation.

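### Part B gives two minimum times for the B1-to-B2 decision (7 days post-treatment, or Day 9), and the earlier can fall before PK stopping criterion (h) can be fully assessed

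*Protocol*

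**What the plan says.** **Timing of the Part B decision**

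- Protocol 3.1, Part B, with the same wording in the synopsis and SAP 3.2: the decision is "made by the study SRC after safety review of available information 7-day post treatment period". No visit is named.
- The paragraph before it: "Participants will be followed up for 21 days to assess post-treatment safety". Protocol 4.3.7, on Day 14: "A Follow-up visit will be performed 1 week (FU1) after last day of study drug administration".
- Protocol 3.1, NOTE item (2), also in the synopsis, sets a condition that must be met before any decision: "All such participants have completed Treatment Visit 5 (Day 7) (for SAD-Part A) and Treatment Visit 9 (Day 9) (for MAD-Part B"), or have withdrawn. Table 4-2 labels T9 as "Day 9 (48 hours after last dosing").

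**Data required for the decision**

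- NOTE item (3): "The SRC will review the available safety data and recommend further dose escalation".
- Protocol 8.6: "the safety data from all participants of each completed cohort will be reviewed by the SRC prior to enrolment" of further participants or dose escalation.
- Stopping criterion (h) sets limits on a cohort's mean AUC (385.6 h\*ng/mL) or Cmax (141.8 ng/mL), with single-dose limits of 386.9 h\*ng/mL and 91.7 ng/mL. It does not say which AUC interval is meant. Protocol 2.2.2 lists three (0-t, 0-infinity and 0-tau).
- The one SRC step that names PK data is the opening of Part B from cohorts A1 and A2, and there PK is qualified by *if applicable*.

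**The concern.** The sentence and the NOTE give different earliest times for the same decision, and neither is said to take precedence. The NOTE is the only text that names a visit, so it is the one most likely to be applied, and it allows the shorter wait. At Day 9 the FU1 laboratory tests, ECG, vital signs and physical examination do not yet exist for the last participants dosed.

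Criterion (h) is the only stopping criterion that acts on exposure rather than on an observed event or finding. It therefore depends on assay results being in hand, and none of the listed conditions requires that.

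The step matters. B1 to B2 doubles the daily dose from 0.6 to 1.2 mg/kg in a first-in-human trial. Protocol 1.6 gives a systemic safety margin of 0.952 at 1.2 mg/kg, below 1, and supports that dose on the ground that no unmonitorable systemic toxicity was seen in animals. The observation period and the exposure limit are what deliver that monitoring.

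**Working it through.** No power or error-rate formula applies. The check is study-day arithmetic.

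**Inputs.** Part B dosing Day 1 to Day 7; T9 = Day 9; FU1 = Day 14 ±1; FU2 = Day 28 (Protocol 3.1, Table 4-2). PK sampling from Protocol 3.1.

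**The plan's own figures**

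- NOTE item (2): last dose Day 7 + 48 h = Day 9, which agrees with T9.
- Part B PK samples: Day 1 (1 + 8) + Day 7 (1 + 10) + 5 pre-dose = 25, as stated.

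**Where does a 7-day post-treatment period end?**

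| Count from | Support in the documents | 7 days ends |
|---|---|---|
| Last dose, Day 7 | 7 + 21 = 28 = FU2; 4.3.7 puts FU1 one week after the last dose | 7 + 7 = Day 14 |
| End of treatment, Day 9 | Synopsis duration: 9-day treatment period, then up to 19 days (9 + 19 = 28) | 9 + 7 = Day 16 |
| First dose, Day 1 | None; Day 8 is only one day after the last dose | 1 + 7 = Day 8 |

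The last-dose count is the best supported, because the sentence immediately before uses it. The end-of-treatment count widens the gap. Only the first-dose count removes it, and that does not fit a post-treatment period after seven daily doses.

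**Size of the gap**

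- Nominal: 14 − 9 = 5 days.
- With the FU1 window: 13 − 9 = 4 to 15 − 9 = 6 days.
- Post-dose observation for the last participant: 2 days at Day 9, 7 days at Day 14.
- Part A for comparison: dose on Day 1, 1 + 7 = Day 8, against T5 on Day 7, a difference of 1 day. The timing conflict of any size is in Part B.

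**PK available for the multiple-dose limits of (h)**

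- AUC to 24 h after the Day 7 dose: sample on Day 8, which is 9 − 8 = 1 day before a Day 9 decision and 14 − 8 = 6 days before a Day 14 decision.
- AUC using the 48 h sample: drawn on Day 9, so 9 − 9 = 0 days or 14 − 9 = 5 days.
- Cmax: normally needs samples only to 10 h on Day 7, 48 − 10 = 38 h before a Day 9 decision.
- The Day 1 profile is complete at the Day 2 pre-dose sample, 9 − 2 = 7 days before Day 9, but it shows first-dose exposure only.
- Part A: the last sample is at 48 h (Day 3), 7 − 3 = 4 days before the Day 7 condition.

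**The case against.** **NOTE item (2) is a floor, not an instruction to decide on Day 9.** That stands. Waiting to Day 14 satisfies both texts on the last-dose count. A reader might infer that the protocol cannot be followed as written; it can. The defect is two different minimum times with no rule on which governs.

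**The 7-day phrase may be Part A wording carried over.** In both parts the NOTE uses the end-of-treatment visit, and the other sentence asks only for available information. This is a plausible account of how the mismatch arose. It does not resolve it: Day 9 is not 7 days post-treatment on either supported count, and latitude on how complete the data are does not shorten the stated period.

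**Day 14 is not the only anchor.** That also stands. The synopsis supports a count from end of treatment, giving Day 16.

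**The gap could be read as 3 to 7 days**, using the ±1 day window that Table 4-2 also gives T9. The documents do not support that range in practice: participants are confined until Day 9, and the 48 h PK sample has a window of ±10 minutes. Two days of observation is also the minimum, for the last participant; those dosed earlier have more.

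**Criterion (h) already implies PK evaluation.** It does, so a reader should not infer that the sponsor plans to escalate without looking at exposure. What is missing from the text supplied is a condition that results be available first. Figure 3-1 and the separate PK analysis plan, to which SAP 4.4 and 7.5 refer, could contain one.

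**Criteria (a) to (g) still operate at Day 9.** They do, on data that include the T8 and T9 laboratory tests and ECGs.

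**Conclusion.** The concern holds as an inconsistency that should be fixed. For the B1-to-B2 decision the documents give Day 14 (or Day 16 on the end-of-treatment count) and Day 9 as minimum times. The SRC may therefore decide about 5 days earlier than the 7-day wording implies (4 to 6 with the FU1 window), and before one full safety visit for the last participants. PK results are not a stated precondition, so the decision can come before the multiple-dose AUC limit of (h) can be assessed.

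This rests on counting post-treatment time from the last dose, on T9 falling on Day 9, and on the text supplied; Figure 3-1 or the PK plan could narrow the PK part.

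Three stronger readings are not supported. Different sites acting differently is not at issue: there is one center, and one SRC takes one decision. The unnamed AUC interval is a missing detail to settle in the same amendment, not a separate defect. And nothing here shows that criterion (h) would be ignored.

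**What to change.** 1. In NOTE item (2) of Protocol 3.1 and the synopsis, change the Part B condition from Treatment Visit 9 (Day 9) to completion of FU1 (Day 14). If Day 9 is what the sponsor intends, correct the 7-day wording in the synopsis, Protocol 3.1 and SAP 3.2 instead, and give the reason.
2. Amend NOTE item (3) and Protocol 8.6 so that no escalation decision is made until the completed cohort's mean AUC and Cmax in MBS-COV recipients have been compared with (h). Report the result to the SRC in a way that protects the blind, since SAP 3.1 places the site investigator on that committee.
3. In the same amendment, state the AUC interval to which the limits of (h) refer; the sponsor must supply it, as the documents do not. In the sentence on opening Part B, restrict *if applicable* to a premature safety stop. Do not delete it, because that sentence also covers a stop at which PK data may not exist.

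Items 2 and 3 apply whichever option is taken in item 1.

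Cost: amendment wording, about 5 days before B2, and assay turnaround between cohorts. The turnaround is not stated and may exceed 5 days. No change to sampling is needed.

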3. STUDY DESIGN

3.1. GENERAL SCHEMA

This is a Phase I, randomized, double-blind study designed to evaluate the safety, tolerability, and PK of inhaled MBS-COV in healthy adult participants in the part A and part B of the study. A total of 44 male and female healthy participants will be enrolled. All participants, after signing the Informed Consent Form (ICF), will be assessed during the screening phase. Only those participants who successfully complete the screening phase and meet the study eligibility criteria will be enrolled. MBS-COV will be administered via inhalation through a portable nebulizer.

Part A (SAD phase)

Part A is randomized, blinded study of a single ascending dose (SAD) phase to evaluate the safety, tolerability and PK of inhaled MBS-COV in healthy participants.

All participants will have a screening visit within 28 days of check-in (Day -1) to determine eligibility. Eligible participants will be admitted to the study center on study Day -1 at which point their eligibility to participate in the study will be confirmed. Only those participants who successfully complete the screening phase and meet the study eligibility criteria will proceed to be randomized to receive a single dose of MBS-COV or placebo in the morning of Day 1 at the assigned dose.

Participants will be assigned to one of up to three doses of MBS-COV (0.3 mg/kg, 0.6 mg/kg, 1.2 mg/kg) to be treated sequentially with increasing doses. Each cohort will include eight (8) participants (6 active and 2 placebo) per below table:

Table 3-1: SAD Phase Cohorts

Cohort		Number of Participants	MBS-COV Dose (mg/kg)	Frequency of Dose
SAD Phase	A1	6 (MBS-COV) +2 (placebo)	0.3	Single Administration
	A2	6 (MBS-COV) +2 (placebo)	0.6	Single Administration
	A3	6 (MBS-COV) +2 (placebo)	1.2	Single Administration

SAD phase will include a sentinel design in which two (2) participants at the given cohort dose be initially enrolled. If the dose can be well tolerated for 48 hours after full administration per site Principle Investigator's judgement, the remaining 6 participants will be enrolled to receive a single dose of MBS-COV at the same dose.

The decision for cohort (dose level) escalation to the higher dose levels will be made by the study SRC after safety review of available information 7-day post treatment period. The data from SAD phase will be reviewed for safety trends to start MAD phase.

Part B (MAD Phase)

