4. STUDY SCHEDULE

4.1. OVERVIEW

The study Schedule of Assessments in presented in [Table 4-1](#) (Part A) and Table 4-2 (Part B). See [Section 7](#) for a detailed description of each protocol assessment and procedure.

The study is divided into three phases: Screening Phase, Treatment Phase, and Follow-Up Phase.

Table 4-1: Schedule of Assessments – Part A (SAD Phase)

Procedure/Assessments	Screening Phase	Treatment Phase							Follow-Up Phase			
		Inpatient Visit				Outpatient Visits						
		Visit	SV	T0	T1 (Baseline)		T2	T3	T4	T5 (EOT/ET)	FU1	FU2 ^[19]
					(Pre-Rx)	(Post-Rx)						
Day	Up to -28	Day -1		Day 1			Day 2	Day 3 (48 hours after dosing)	Day 4	Day 7	Day 14	Day 28
Window Period				Within 28 days of the Screening Visit			NA	NA	NA	±1	±1	±1
ASSESSMENTS												
Informed Consent ^[1]	X											
Eligibility Evaluation ^[2]	X	X										
Participant Demographics	X											
Medical History ^[3]	X	X	X									
Physical Examination	X		X	X ^[4]	X ^[4]	X ^[4]	X ^[4]	X ^[4]	X ^[4]	X		
Height, Weight and BMI	X											
Vital Signs	X	X	X	X ^[5]	X	X	X	X	X	X		
12-lead ECG	X	X	X	X ^[6]	X	X	X	X	X	X		
Chest X-ray	X								X			
Spirometry assessments ^[7]	X	X		X								
Participant Confined to Research Clinic		X	X	X	X							
Participant Discharge from Research Clinic (if applicable) ^[8]							X					
Randomization			X									
Concomitant Medications	X	X	X	X	X	X	X	X	X	X		
Adverse Events				X	X	X	X	X	X	X		
LABORATORY TESTS^[9]:												
Hematology ^[10]	X	X			X	X			X	X		
Biochemistry ^[11]	X	X			X	X			X	X		
Coagulation Indices ^[12]	X	X			X	X			X	X		
Serum/Urine Pregnancy Test ^[13]	X	X							X	X		
Urinalysis ^[14]	X	X			X	X			X	X		

Procedure/Assessments	Screening Phase	Treatment Phase								Follow-Up Phase			
		Inpatient Visit				Outpatient Visits							
		Visit	SV	T0	T1 (Baseline)		T2	T3	T4	T5 (EOT/ET)	FU1	FU2 ^[19]	
					(Pre-Rx)	(Post-Rx)							
Day	Up to -28	Day -1	Day 1		Day 2	Day 3 (48 hours after dosing)	Day 4	Day 7	Day 14	Day 28			
Window Period			Within 28 days of the Screening Visit		NA	NA	NA	±1	±1	±1			
Nasopharyngeal or nasal swab for COVID-19 ^[15]	X	X				X	X	X	X	X			
Urine Drug and Alcohol Screening	X	X											
PK evaluations ^[16]			X	X	X	X							
ADA ^[17]			X							X	X		
Screening for infectious diseases (HIV antibody; HbsAg; HCV antibody)	X												
INTERVENTION(s):													
MBS-COV Administration ^[18]			X										

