- [1] Informed consent must be obtained prior to participation in any protocol-related activities that are not part of routine care.
- [2] Initial evaluation of participant eligibility will be performed by Investigator.
- [3] Medical history and current therapies (medications and non-medications).
- [4] Symptom-directed physical examination.
- [5] Vital signs will include blood pressure, pulse, respiration rate, and temperature. On treatment visits will be conducted three times a day, within 120 minutes before administration, within 1 hour after administration, and 4-6 hours after administration, respectively. On other visits will be conducted once during the visit.
- [6] 12-lead ECG on treatment visits will be conducted three times a day, within 120 minutes before administration, within 1 hour after administration, and 4-6 hours after administration, respectively. On other visits will be conducted once during the visit.
- [7] Spirometry assessments will be started 5 minutes after the dosing with frequent spirometry measurements at 5 (± 1 min), 15 (± 1 min), 30 (± 5 min), 60 minutes (± 5 min). On other visits will be conducted once during the visit. If spirometry is completed within 7 days prior to dosing, this assessment does not need to be repeated on Day-1.
- [8] Participants will be discharge from the clinic when all required assessments for T3 Day (3) are performed.
- [9] If hematology, biochemistry, coagulation and urinalysis are completed within 7 days prior to dosing, this assessment does not need to be repeated on Day-1.
- [10] Hematology
Hemoglobin, Hematocrit (HCT), Red Blood Cells (RBC), White Blood Cells (WBC) with total and differential count, Absolute Neutrophil Count (ANC) and platelets.
- [11] Biochemistry
Hepatic function indicators: total bilirubin, alkaline phosphatase, aspartate aminotransferase (AST), alanine aminotransferase (ALT), total protein, albumin, Lactate dehydrogenase (LDH), amylase and lipase

Renal function indicators: Serum creatinine, eGFR

Electrolytes: sodium, potassium, chloride, calcium and bicarbonate

Other: glucose (random), triglyceride (TG), cholesterol (total), Creatine kinase.

[12] Coagulation

Prothrombin time (PT), activated partial thromboplastin time (APTT), thrombin time (TT), fibrinogen (FIB)

[13] Serum pregnancy test in screening visit (Will include FSH and estradiol levels at screening for post-menopausal women only) and EOT, and Urine pregnancy test in other visits.

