4.2.3. Part A (SAD) - Treatment Visit 1: Baseline Visit (T1: Day 1)

The first assigned study treatment dose will be administered after completion of all study evaluations. Adverse events and changes in concomitant medications will be collected. Participants in Cohorts A1 to A3 will be inhaled a single dose of MBS-COV or placebo through a portable nebulizer on Day 1.

The following assessments will be performed:

- Medical history (pre dose)
- Vital signs (pre and post dose) (Vital signs will include blood pressure, pulse, respiration rate, and temperature. On treatment visits will be conducted three times a day, within 120 minutes before administration, within 1 hour after administration, and 4-6 hours after administration, respectively.)
- Randomization (pre dose)
- Physical examination (pre and post dose)
- 12-lead ECG (pre and post dose) (12-lead ECG on treatment visits will be conducted three times a day, within 120 minutes before administration, within 1 hour after administration, and 4-6 hours after administration, respectively.)
- List concomitant medications
- PK timepoints: Cohorts A1 to A3: For the single dose on day 1, blood samples will be collected before dosing, and afterwards at 5 min (± 1 min), 15 min (± 2 min), 0.5 h (± 2 min), 1 h (± 5 min), 2 h (± 5 min), 4 h (± 5 min), 8 h (± 10 min), 10 h (± 10 min) after dosing.
- ADA timepoints: Blood samples will be collected on Day 1 before dosing
- Spirometry Assessment (Spirometry assessments will be started 5 minutes after the dosing with frequent spirometry measurements at 5 (± 1 min), 15 (± 1 min), 30 (± 5 min), 60 minutes (± 5 min).)

- Adverse events evaluation after first dose
- Participants will be confined till 24 hours pharmacokinetic samples are obtained following study drug administration.

4.2.4. Part A (SAD) – Treatment Visit 2 to Treatment Visit 5/End of Treatment (T2: Day 2 to T5: Day 7)

The following assessments will be performed (refer to the schedule of events Table 4-1)

- Vital signs
- Physical examination, including dermatologic examination
- 12-lead ECG
- List concomitant medications
- Laboratory assessments (hematology, chemistry, coagulation and urine analysis) (T2, T3, and T5 only)
- Chest X-ray (T5 only)
- PK timepoints: Cohorts A1 to A3: For the single dose on day 1, blood samples will be collected at 24 h (\pm 10 min) and 48h (\pm 10 min) after dosing.
- Serum pregnancy test only on T5 (EOT)
- Adverse events evaluation

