- Nasopharyngeal or nasal swab for COVID-19 (T3, T4 and T5)
- Participants will be discharged from the clinic on Day 3. if applicable.

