3.1. Part A: SAD phase

Part A includes 3 dose-escalation cohorts (0.3 mg/kg, 0.6 mg/kg, 1.2 mg/kg MBS-COV or placebo). Each cohort will include 8 participants (6 active and 2 placebo) per below table:

| Cohort | MBS-COV Does Active:placebo | Frequency of Does |
|--------|--------------------------------|-----------------------|
| A1 | 0.3 mg/kg (6:2) | Single Administration |
| A2 | 0.6 mg/kg (6:2) | Single Administration |
| A3 | 1.2 mg/kg (6:2) | Single Administration |

From the perspective of safety, sentinel dosing will be used in each cohort, and the first 2 subjects in each cohort will be randomized 1:1 to MBS-COV or placebo. If the dose can be well tolerated for 48 hours after full administration per the study Safety Review Committee (SRC) consisting of the sponsor (designee), site Principle Investigator, and medical monitor, the remaining 6 subjects in the cohort may be randomized 5:1 to MBS-COV or placebo.

All participants will have a screening visit within 28 days of check-in (Day -1) to determine eligibility. Eligible participants will be admitted to the study center on study Day -1 at which point their eligibility to participate in the study will be confirmed. Only those participants who successfully complete the screening phase and meet the study eligibility criteria will proceed to be randomized to receive a single dose of MBS-COV or placebo in the morning of Day 1 at the assigned dose.

The decision for cohort (dose level) escalation to the higher dose levels will be made by the study SRC after safety review of available information 7-day post treatment period. The data from SAD phase will be reviewed for safety trends to start MAD phase.

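### The protocol gives two discharge times for Part A (Day 2 or the 24 h sample, versus Day 3 after the 48 h assessments), and the earlier one lets sentinels leave halfway through the 48 h tolerability gate

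*Protocol*

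**What the plan says.** The protocol gives two different end points for the Part A stay.

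**Earlier release**
- Section 3.1, Study Visits, Treatment Visit 0 (repeated in the synopsis): "confined to research clinic until Day 2 for cohort A1 to A3 (SAD phase".
- Section 4.2.3: "Participants will be confined till 24 hours pharmacokinetic samples are obtained following study drug administration".

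**Later release**
- Table 4-1, footnote 8: "Participants will be discharge from the clinic when all required assessments for T3 Day (3) are performed". The column heading for T3 is "Day 3 (48 hours after dosing".
- Section 4.2.4: "Participants will be discharged from the clinic on Day 3. if applicable".

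The synopsis, under Study Duration, also gives a Part A in-unit stay of 3 days.

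The sentinel rule in section 3.1 has two participants dosed first in each cohort. The other six follow "If the dose can be well tolerated for 48 hours after full administration". SAP section 3.1 adds that "the first 2 subjects in each cohort will be randomized 1:1 to MBS-COV or placebo". Neither document sets a separate or longer stay for sentinels, and the SAP names no discharge day.

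**The concern.** This is the first human exposure to the product (protocol section 1.4.2), and each cohort's remaining six participants are dosed on the strength of two sentinels, only one of them on active drug under the SAP's allocation. If the site follows section 4.2.3, those sentinels can go home at 24 h, and the second half of the gate then depends on what they notice and report from outside until they return on Day 3.

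The protocol itself gives reasons to want supervision in that window:
- Table 1-1 reports lung half-lives in hamsters of about 61 to 74 h at the lower dose and 152 to 183 h at the higher dose.
- Section 1.6 calculates a systemic safety margin of 0.952 at 1.2 mg/kg.
- Scheduled post-dose spirometry in Part A ends 60 minutes after dosing (Table 4-1, footnote 7). Repeat spirometry is at the investigator's discretion (section 7.11) and is easier to obtain from someone still in the unit.

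There is also a plain compliance problem. Whichever rule the site follows, it departs from another sentence of the same protocol.

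**Working it through.** There is no stated figure to reproduce. The check sets the texts side by side and does short arithmetic.

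**1. Are the rules compatible?** Section 4.2.3 ends the stay at the 24 h sample. Footnote 8 ends it after all T3 assessments, at 48 h. The two differ by 48 − 24 = 24 h. Footnote 8 carries no qualifier, so the closing qualifier in section 4.2.4 does not reconcile them.

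**2. Which rule is more likely intended?** The synopsis gives 3 in-unit days for Part A and 9 for Part B. Part B participants are admitted on Day -1 and discharged on Day 9, and there is no Day 0.

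| Counting method | Part B, Day -1 to Day 9 | Part A to Day 2 | Part A to Day 3 |
|---|---|---|---|
| Calendar days including Day -1 | 10 | 3 | 4 |
| Days from Day 1 | 9 | 2 | 3 |
| Nights | 9 | 2 | 3 |

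Taken alone, 3 in-unit days fits either rule: Day -1 to Day 2 is 3 calendar days. But Part B's stated 9 rules out counting Day -1 as a calendar day. By either method that gives 9 for Part B, a 3-day Part A stay ends on Day 3. This is an inference from consistent counting; no text states the convention.

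**3. How many participants does the gate concern?**
- Sentinels: 2 per cohort × 3 cohorts = 6. This is a maximum, because section 3.1 allows up to three doses.
- On active drug at 1:1 (SAP only): 6 × 1/2 = 3.
- Other Part A participants: 24 − 6 = 18. Their discharge rule is also unclear, but the sentinel gate does not rest on them.

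**4. How much of the gate falls inside the unit?**
- Section 4.2.3, release at the 24 h sample: 24/48 = 50%, leaving 24 h outside.
- Section 3.1, if Day 2 is read as the end of that day and dosing is assumed at 08:00 to 10:00 on Day 1: 38 to 40 h inside, that is 38/48 = 79% to 40/48 = 83%, leaving 8 to 10 h outside.
- Footnote 8: 48/48 = 100%.

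At the earliest release, with all three cohorts opened, 6 × 24 = 144 of 6 × 48 = 288 sentinel-hours fall outside the unit, the same 50%.

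**5. What is measured under either rule?** Section 4.2.4 schedules vital signs, ECG, adverse-event review and the 24 h and 48 h PK samples. Its laboratory line reads "Laboratory assessments (hematology, chemistry, coagulation and urine analysis) (T2, T3, and T5 only". The T3 assessments therefore take place whether the sentinel is still in the unit or returns for the visit.

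The discharge row of Table 4-1 was not used as evidence, because its columns are displaced in the text available.

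**The case against.** The strongest reply is that no stated requirement is breached. The gate asks for 48 h of good tolerability in the investigator's judgement and does not ask for continuous in-unit observation. The most acute hazard the protocol names, bronchospasm, is measured in the first hour, and post-dose vital signs and ECG follow within 1 h and at 4 to 6 h, all in the unit under any reading. The Day 3 assessments happen regardless. Escalation to the next dose still waits for every participant's Day 7 visit (or withdrawal) and committee review. Fifty per cent is the worst case, and a site working from the schedule table would keep participants to Day 3 anyway.

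Much of this stands, and it limits the size of the point. No endpoint, analysis set or escalation criterion changes, and the range in the working belongs beside the 50%. The qualifier in section 4.2.4 also looks like template wording, since it follows the Part B Day 9 discharge as well.

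It does not remove the conflict. The protocol gives no order of precedence between the table footnote and the visit text, so section 4.2.3 is as operative as footnote 8. Under the most generous reading of Day 2, part of the gate still falls outside the unit. And the decision at stake is not only escalation: the gate opens dosing of six more people at the same dose, well before the Day 7 review.

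**Conclusion.** The inconsistency is real and lies in the current protocol text. One of the two rules lets up to 6 first-in-human sentinels, 3 on active drug under the SAP's allocation, leave the unit 24 h into a 48 h gate. In-unit coverage of the gate is 50% at the earliest release, about 79 to 83% if Day 2 means the end of that day with morning dosing as assumed, and 100% under footnote 8. What is lost is supervision between 24 and 48 h, not scheduled data. Day 3 is most likely the intended rule, given footnote 8, section 4.2.4 and the in-unit count. The correction should be made, because a site can in good faith follow the weaker rule; it does not call the study's analysis into question.

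**What to change.** Adopt Day 3 throughout Part A:
- In the synopsis and section 3.1 (Treatment Visit 0), replace the Day 2 limit with confinement until all T3 assessments (Day 3, 48 h) are complete.
- In section 4.2.3, replace the 24 h sample as the end of confinement with completion of all T3 assessments, including the 48 h PK sample and, for sentinels, the 48 h tolerability assessment.
- Add one sentence saying that the qualifier on discharge in section 4.2.4 and Table 4-1 does not allow sentinels to leave before T3 is complete.
- State how the 3 in-unit days in the synopsis are counted.

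The cost is wording in three places plus two short clarifications. If the site had planned on Day 2 discharge, it adds at most one night per participant, or 24 × 1 = 24 nights across Part A; footnote 8 already requires that night. If the sponsor wants earlier release for the other 18 participants, it should say so explicitly, amend footnote 8 and section 4.2.4 to match, and keep the Day 3 rule for the sentinels.
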